7.4 Concomitant Medications

7.4.1 Medications Permitted

All medications including prescription, over-the-counter, and natural remedies, that the subject has taken within 28 days prior to Visit 1 or during the study will be recorded in the CRF and in the subjects' source documents. The name of the drug, dose, route of administration, duration of treatment (including start and stop dates), frequency, and indication will be recorded for each medication. The use of fluorescein and lissamine green do not need to be recorded on the concomitant medications page.

Subjects should use medications consistently throughout the study and for 28 days prior to Visit 1 with the exceptions outlined in [Section 7.4.2](#).

7.4.2 Medications Not Permitted

Use of the following products on visit days, while in the clinic, and for at least 6 hours after dosing will not be allowed (use of these all other times during the study is permitted):

- Topical ocular medications including artificial tears, topical steroids, Restasis®, Xiidra®, autologous serum, and lid wipes and scrubs.
- Contact lens wear

Use of the following medications during the study will NOT be allowed within 14 days of Visit 1 or during the study:

- Oral, nasal and ocular antihistamines
- Oral or topical secretagogues such as pilocarpine or Evoxac
- Topical anti-glaucoma medications

Use of the following medications during the study or within 28 days prior to Visit 1 will NOT be allowed:

- Investigational product or device

Use of the following medications during the study or within 3 months prior to Visit 1 will NOT be allowed:

- Botulinum toxin (Botox® or equivalent) injection in the periocular region

7.5 Treatment Compliance

Because this is a single day crossover, with study medication administered by the PI or clinical site personnel, treatment compliance will not be calculated. Time of administration of study medication and kit number will be captured in the CRF.

7.6 Drug Accountability

Study medication accountability will occur during monitoring visits by Parion Sciences, Inc, or its designee. Accountability will be ascertained by performing reconciliation between numbers of Kits/bottles of study medication received on site/compounded for distribution, number of bottles dispensed to subjects according to the protocol-specified dosing regimen, and the remaining unused study medication at the time of reconciliation.

Clinical trial materials and bulk supplies will be shipped to the investigational site/pharmacy under sealed conditions. Study medication shipment records will be verified by comparing actual quantity of drug received against the shipment inventory sheet accompanying the drug received at the site. Accurate records of receipt and disposition of the study medications (e.g., dates, quantity, subject number, dose dispensed, returned, etc.) must be maintained by the investigator or his/her designee. Study medication will be stored at the site in an area free of environmental extremes, at controlled temperatures between 2 – 8°C (36 - 46°F). This area should be limited and have controlled access.

At the end of the study, all study materials, including unused study medication bottles and bulk supplies will be returned to Parion Sciences, Inc. (or its designee) for disposal. The study monitor or designee should verify drug accountability at routine monitoring visits.

7.7 Maintenance of Randomization and Procedure for Breaking the Code

The treatment assignments will be masked to the investigator, medical monitor, study site personnel, subjects in the study and those involved in the conduct of the study.

Only in the case of a medical emergency, or occurrence of a suspected related, unexpected, SAE, may the randomization code be unmasked and made available to the investigator, medical monitor, subject, and/or other personnel involved in the monitoring or conduct of this study. In the absence of medical need, the randomization code will not be available to the above personnel until after the study is completed and the database is locked.

The Data Review Group will review unmasked data. The Medical Monitor and Principal Investigator (or designee) and members of the Parion team not involved in the conduct of the study will be unmasked as part of the Data Review Group for decision making on the strength of P-321 Ophthalmic Solution to be used in Phase 2 of the study. The treatment assignments will remain masked to subjects in the study, the clinical monitor, and other site and Parion Sciences personnel involved in the conduct of the study and not involved in the Data Review Group. Additional unmasked reviews of subject data may occur throughout the study to make recommendations on further dose adjustments and for planning purposes. These reviews will follow the procedures outlined in [Section 6.5](#).

For Phase 1, a randomization list will be generated and the kits will be labeled in a masked fashion. The randomization assignments will be kept in a secure area at Parion Sciences, Inc. or designee. For Phase 2, a randomization list will be provided to the pharmacy and the pharmacy will distribute the assigned drug according to the randomization schedule with subjects remaining masked.

In case of a medical need, the investigator will treat the subject as needed regardless of randomized treatment. Since there is no specific antidote to P-321 Ophthalmic Solution, immediate emergency unmasking is not necessary. If the investigator feels it is necessary to unmask a subject's treatment assignment after an emergency situation, the investigator must call the medical monitor and notify Parion Sciences, Inc. The treatment assignment will be revealed on a subject-by-subject basis, leaving the masking of the remaining subjects intact.

8 STATISTICS

8.1 Statistical Methods

8.1.1 Subject Disposition, Demographic and Background Characteristics

Subject disposition, demographic, and background characteristics will be summarized by using descriptive statistics. Baseline homogeneity with respect to demographic and background characteristics will be assessed via an overall F-test from analysis of variance (ANOVA). For categorical variables, treatment differences will be assessed using the chi-square test or Cochran Mantel Haenszel (CMH) test with modified ridit scores for ordered categorical variables.

Background characteristics include: demographics, tear volume measurements by UHR-OCT and Keratograph 5M, visual acuity, symptoms upon entry, medical history, concomitant medication use, tear osmolarity, tear break up time, meibomian gland assessments, corneal and conjunctival staining, Schirmer and IOP.

8.1.2 Pharmacodynamic parameters

UHR-OCT will assess the following parameters in both eyes: UTMH, LTMH, UTMV, LTMV, and TTMV (UTMV + LTMV). Treatment group differences for tear volume assessments will be conducted via comparisons of tear meniscus height, and if applicable, tear meniscus volume (TMV). These parameters will be compared between each dose of P-321 Ophthalmic Solution and Placebo using a t-test for study eyes, and for all eligible eyes. Analysis of covariance (ANCOVA) models will be used to adjust for the baseline TMH and TMV for study eyes. For all eligible eyes, a generalized estimation equations (GEE) will also be used to account for the correlation between eyes. For the GEE analysis, an exchangeable correlation matrix will be assumedArea under the curve (AUC) analysis will also be performed as an exploratory analysis to compare OCT assessments and Keratograph 5M LTMH for Placebo vs each dose of P-321.

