Subject disposition, demographic, and background characteristics will be summarized using descriptive statistics. Baseline homogeneity with respect to demographic and background characteristics will be assessed via an overall F-test from analysis of variance (ANOVA). For categorical variables, treatment differences will be assessed using the chi-square test or Cochran Mantel Haenszel (CMH) test with modified ridit scores for ordered categorical variables.

Pharmacodynamic Analysis

Treatment group differences for tear volume assessments will be conducted via comparisons of tear meniscus height, and if applicable, tear meniscus volume (TMV). These parameters will be compared between each dose of P-321 Ophthalmic Solution and Placebo using a t-test for study eyes, and for all eligible eyes. Analysis of covariance (ANCOVA) models will be used to adjust for the baseline TMH and TMV for study eyes. For all eligible eyes, a generalized estimation equations (GEE) will also be used to account for the correlation between eyes. For the GEE analysis, an exchangeable correlation matrix will be assumed.

Safety

All safety analyses will be included for all subjects who were randomized and received at least one dose of study medication.

The incidence of AEs will be tabulated by treatment group, by treatment sequence, by severity, and by relationship to study medication.

TABLE OF CONTENTS

SUMMARY OF CHANGES TO THE PROTOCOL.....	3
1 PROTOCOL SYNOPSIS.....	4
2 BACKGROUND INFORMATION	13
2.1 Description of Study Medication	13
2.2 Non-Clinical Studies for P-321 Ophthalmic Solution	14
2.2.1 Pharmacology	14
2.2.2 Absorption, Distribution, Metabolism, and Excretion.....	15
2.2.3 Toxicology	16
2.3 Clinical Experience with P-321 Ophthalmic Solution.....	17
2.4 Justification for Route of Administration and Dose Selection	17
2.5 GCP Compliance	17
2.6 Population to be Studied	18
3 TRIAL OBJECTIVES AND PURPOSE.....	19
4 INVESTIGATIONAL PLAN.....	20
4.1 Overall Study Design.....	20
4.2 Endpoints	21
4.2.1 Primary Endpoint.....	21
4.2.2 Secondary Endpoints	21
4.2.3 Safety and Tolerability Endpoints	22
4.3 Duration of Participation.....	22
5 SELECTION AND WITHDRAWAL OF SUBJECTS.....	23
5.1 Subject Inclusion Criteria	23
5.2 Subject Exclusion Criteria	23
5.3 Randomization Criteria	24
5.4 Study Eye	25
5.5 Subject Withdrawal Criteria and Stopping Rules	25
6 PROCEDURES.....	26
6.1 Visit 1: Screening (3 to 9 days prior to Visit 2 – Randomization)	26

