4 INVESTIGATIONAL PLAN

4.1 Overall Study Design

This is a single-center, randomized, cross-over, placebo-controlled, Phase 2a trial designed to evaluate the pharmacodynamic effects of tear volume of P-321 Ophthalmic Solution in tear-deficient dry eye subjects. Approximately 24 eligible subjects will complete the study which consists of two Phases: Approximately 8 subjects participating in Phase 1 will receive 0.017% P-321 ophthalmic Solution and Placebo, and the remainder of the 24 subjects participating in Phase 2 will receive either 0.05%, 0.017% or 0.01% P-321 and placebo. The decision on the dose administered in Phase 2 will be made following unmasked data review from subjects in Phase 1. In each Phase, subjects will receive sequentially two treatments: P-321 Ophthalmic Solution (Treatment A) and Placebo (Treatment B). Subjects will be randomly assigned to receive treatment sequence AB or BA, in a 1:1 ratio.

The pharmacodynamic measures of tear volume will be assessed by two methods: UHR-OCT and Keratograph 5M. Optical coherence tomography (OCT) has been used to image the anterior segment of the eye including tears on the ocular surface. The method is non-invasive and non-contact which is suitable for imaging the tear meniscus around both upper and lower lids. The system at Bascom Palmer Eye Institute is a custom made OCT system (UHR-OCT) with an ultra-high resolution (3 μ m). Many previous studies have been done using UHR-OCT and its clinical application has been well documented. With the wide scan of the UHR-OCT, cross-sectional images of the tear menisci can be imaged and tear meniscus volume can be calculated. The Keratograph 5M is a corneal topographer with a built in camera optimized for external imaging. The Keratograph 5M has a feature that enables the non-invasive assessment of the tear meniscus height of the inferior eyelid from high resolution images obtained under infrared light. With the use of a built-in measurement tool the height of the tear meniscus is obtained.

The study will consist of three study visits: a Screening Visit (Visit 1), and two treatment visits (Visit 2 and Visit 3). The duration of the study may be up to 23 days.

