5 SELECTION AND WITHDRAWAL OF SUBJECTS

5.1 Subject Inclusion Criteria

Subjects must meet the following criteria at Screening to be enrolled in the study:

1. Provide written informed consent
2. Male or female subjects aged 18 to 80 years
3. Are willing and able to follow instructions and can be present for the required study visits for the duration of the study
4. Have a history of predominantly tear-deficient dry eye of mild to moderate severity, in both eyes, supported by a previous clinical diagnosis
5. Subjects must have in at least one eye an average tear meniscus height (TMH) of the lower eye lid of 210 μm or less as assessed by UHR-OCT
6. Have normal lid anatomy
7. Female subjects of child bearing potential must have a negative serum pregnancy test at Screening and agree to use a medically acceptable form of birth control (e.g., intrauterine device, birth control pill, patch or subcutaneous implant, condoms, diaphragm, or abstinence) throughout the duration of the study. Females who are breast feeding an infant are not eligible to participate in the study.
8. Subjects must:
 - a. Remain on current medications for the duration of the study
 - b. Be on the current medication regimen at least during the past 28 days
 - c. Be able to withhold ocular topical medications, including artificial tears, topical steroids, Restasis[®], Xiidra[®], autologous serum, and lid wipes and scrubs on visit days while in the clinic, and for at least 6 hours after dosing with study medication
 - d. If they are contact lens wearers, be able to withhold wearing contact lenses on visit days, while in the clinic, and for at least 6 hours after dosing

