5.4 Study Eye

The Study eye will be the eye that meets entry criteria as defined in [Section 5.1](#), [Section 5.2](#), and [Section 5.3](#). If both eyes meet entry criteria, the study eye will be the eye with the lower average TMH by OCT. If both eyes have the same average TMH, then the qualifying study eye will be the **right eye**.

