6.2 Visit 2: First Treatment Visit (3 -9 days after Visit 1)

The following procedures will be completed at Visit 2 which will take place between 8:00AM and 11:00 AM and at approximately the same time as Visit 1:

- Subjects will be asked to remain on site through this visit and limit use of devices with video display screens.
- Confirm continued eligibility through review of inclusion and exclusion criteria as outlined in [Sections 5.1 and 5.2](#) of the protocol with the exception of the inclusion criteria #5 (UHR-OCT dry eye).
- Review of concomitant medications and medical changes since last visit
- Administer symptom questionnaires (SPEED, OSDI, and SANDE Part 1 and Part 2) before other procedures and before dosing
- Assess adverse events since the last visit and during this visit
- Collect vital signs (pulse, blood pressure, temperature and respiration rate) pre-treatment
- Conduct pretreatment measurements in both eyes by UHR-OCT and Keratograph 5M (at approximately the same time as conducted at Visit 1) immediately prior the administration of study medication. UHR-OCT will be conducted first, immediately followed by Keratograph 5M.
- Subjects will be assigned a treatment number at this visit.
- Administer one drop of assigned study medication in each eye immediately after the pretreatment assessment (the drug administration will be conducted by the PI or clinical site personnel). NOTE: Remove study medication from refrigerator at least 15 minutes prior to administration.
- At approximately 5 minutes after drug administration, administer drop instillation comfort assessment
- Repeat assessments by UHR-OCT and Keratograph 5M post dose at 15 ± 5 minutes, 30 ± 10 minutes, 1 hour ± 20 minutes, 2 hours ± 30 minutes, 4 hours ± 30 minutes, and 6 hours ± 30 minutes.
- Immediately prior to the 2 hour time point for tear volume measurement, a post instillation dry eye symptom assessment will be completed
- After the 6-hour tear volume assessment, conduct a biomicroscopy and external examination
- At the end of the visit, the subject will be instructed to return to the clinic between 7 and 14 days for the second treatment (Visit 3, Second Treatment Visit) with the visit occurring in the AM, at approximately the same time of day as Visit 1 and Visit 2

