8.2 Sample Size Estimation

An initial sample size of approximately 24 subjects is proposed for this study. The study design includes OCT measurements at time 0 (pretreatment) and post dose at 15 minutes, 30 minutes, 1 hour, 2 hours, 4 hours and 6 hours. Shen et al. ([Shen, 2009](#)) reported that among the measures of tear volume and tear film thickness obtainable through OCT, the most sensitive and specific measure of dry eye is the low tear meniscus height (LTMH). Power estimations for a two-period, two-treatment, two-sequence crossover design (2x2x2), this study size when all subjects treated with P-321 are analyzed, will provide 98% power to detect a difference of 60 μm at 1 hour or a power of 99% if the average increase in LTMH over the six hours is 60 μm (assuming within-subject SD of 71). In this study it is expected that the drug will reach its peak effect at 1 hour post dose and that the effect diminishes at hours 4 and 6 (to values still above pre-dose values).

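### The t-test on all eligible eyes counts a subject's two eyes as independent, and the pharmacodynamic tests are not stated to be paired or adjusted for period

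*Combined protocol and SAP*

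**What the plan says.** Section 8.1.2 compares tear meniscus height and, if applicable, volume "compared between each dose of P-321 Ophthalmic Solution and Placebo using a t-test for study eyes, and for all eligible eyes". The synopsis repeats this: "using a t-test for study eyes, and for all eligible eyes". Section 8.1.2 adds an ANCOVA on baseline for study eyes. For all eligible eyes, "a generalized estimation equations (GEE) will also be used to account for the correlation between eyes", with an exchangeable correlation matrix.

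Inclusion criterion 5 (section 5.1) requires only one eye at or below the 210 µm limit, and section 5.4 provides for two: "If both eyes meet entry criteria, the study eye will be the eye with the lower average TMH by OCT". Treatment is bilateral. Section 6.2 reads "Administer one drop of assigned study medication in each eye immediately after the pretreatment assessment", and section 6.3 does the same for the second period. Under section 4.1, "Subjects will be randomly assigned to receive treatment sequence AB or BA, in a 1:1 ratio".

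Section 8.2 bases its power on a two-period, two-treatment crossover with about 24 subjects. Section 8.3 tests each hypothesis at 0.05. A check for sequence or period effects appears only in section 8.1.4, for safety. For the pharmacodynamic tests, no section states pairing or names a subject, period or sequence term. The GEE's cluster, variance estimator and reference distribution are not given either.

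**The concern.** Two eyes of one person, dosed together and measured minutes apart, do not carry the information of two people. A t-test over all eligible eyes assumes that they do. The plan recognises the correlation, since it gives it as the reason for the GEE, yet it keeps the t-test alongside and does not say which result governs. If the two disagree, the t-test could be reported at a level it does not have.

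The silence on pairing is a second gap. The crossover was chosen so that each subject serves as their own control. An unpaired test would put the between-subject variance back into the error term and lose the precision on which section 8.2 relies.

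**Working it through.** **Inputs from the documents.** About 24 subjects (about 8 in Phase 1), a 60 µm difference at 1 hour, SD 71 labelled within-subject, alpha 0.05 (taken as two-sided), stated power 98% (sections 4.1, 8.2, 8.3). Inter-eye correlations, between-subject SDs, period effects and the share of subjects with two eligible eyes are assumptions, because the documents give none.

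**1. The plan's own figure.** Reading 71 as the SD of the paired difference, the standard error is 71/√24 = 14.5 and the noncentrality is 60/14.5 = 4.14. On 22 df, power is 97.7%, which reproduces 98%. Reading 71 as the SD of a single within-subject measurement, the SD of the difference is 71 × √2 = 100.4 and power is 79.9%, which does not. The first reading is used below.

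**2. All-eyes t-test, paired by eye.** Let ρ be the correlation between a subject's two eyes in the treatment difference. With n subjects and two eyes each, the mean difference has variance σ²(1+ρ)/(2n), while the test estimates about σ²/(2n). The large-sample type I error is therefore 2 × [1 − Φ(1.96/√(1+ρ))]. Simulation (40,000 replicates per cell) agrees closely:

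| ρ | Formula | 8 subjects | 16 subjects | 24 subjects | Half with two eyes (8 to 24 subjects) |
|---|---|---|---|---|---|
| 0.3 | 8.6% | 8.7% | 8.7% | 8.5% | 7.0–7.3% |
| 0.5 | 11.0% | 11.2% | 11.2% | 11.1% | 9.0–9.2% |
| 0.8 | 14.4% | 15.3% | 15.1% | 14.9% | 11.6–11.8% |

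**3. All-eyes t-test, unpaired.** Two errors now pull in opposite directions: ignoring inter-eye correlation makes the standard error too small, and ignoring the subject makes it too large. Let r be the between-subject to within-subject variance ratio, and let ρ be the share of the within-subject variance common to both eyes at a visit. The true variance divided by the variance used is (1+ρ)/(1+r), so in large samples the level is right only if r happens to equal ρ. Simulated type I error with 24 subjects, two eyes each:

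| r | ρ = 0.3 | ρ = 0.8 |
|---|---|---|
| 0.18 | 6.3% | 11.6% |
| 0.5 | 3.6% | 7.9% |
| 1 | 1.8% | 4.6% |
| 2 | 0.5% | 1.5% |

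**4. Study-eye t-test.** There is one eye per subject, so inter-eye correlation does not arise. Paired, with balanced sequences, the simulated level is 4.9–5.1%. With an assumed period effect of 0.5 SD of the difference left unmodelled, it falls to about 3% (conservative). Unpaired, the single-measurement within-subject SD is 71/√2 = 50.2 and the standard error is √(2 × (50.2² + SDb²)/24) on 46 df:

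| Between-subject SD (SDb) | Standard error | Power for 60 µm |
|---|---|---|
| 30 | 16.9 | 94% |
| 50 | 20.5 | 82% |
| 71 | 25.1 | 65% |

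**5. GEE.** If it is clustered on subject and tested with an uncorrected robust z statistic, the balanced-case type I error is 2 × P(t with n−1 df > 1.96 × √((n−1)/n)). This gives 10.9%, 7.7% and 6.8% for 8, 16 and 24 subjects.

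**6. Proposed analysis.** One value per subject per period (mean of eligible eyes), with a period term and a period effect of 0.5 SD present, gives a simulated type I error of 4.8–5.2% in every scenario.

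**The case against.** The plan does not overlook the correlation. The GEE addresses it, and the study-eye t-test and ANCOVA are free of it, so the clustering fault lies in one test among several. Section 8.1.3 says no efficacy endpoints will be formally assessed, in a single-centre Phase 2a study. The higher error rates assume that everyone has two eligible eyes, whereas section 5.1 asks for only one. If a quarter have two, the eye-paired error with 24 subjects is about 6.4%, 7.5% and 8.9% at the three correlations, and if none do it is 5%. The crossover power statement suggests that a paired test was intended. The unpaired powers also use between-subject SDs of raw height, and these would matter less for change from pre-dose. The 65% case is extreme: a uniform spread over 0 to 210 µm has an SD of only 61. The 24 subjects share one dose only if Phase 2 stays at 0.017%. The period term matters little when sequences are balanced: a 20 µm effect lowers power from 97.7% to 96.8%.

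Most of this limits the size and does not remove the fault. Section 8.3 still sets 0.05 for each hypothesis, section 4.2.1 names a primary endpoint and section 8.2 claims power. The test is written into the plan, and pairing it by eye, as many analysts would, is what inflates it whenever some subjects have two positively correlated eyes. The points on period and on probable intent do stand. Unstated pairing, period term and GEE variance would, on their own, be missing detail rather than error.

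**Conclusion.** The concern holds. As written, the all-eyes t-test does not control its 5% level. Paired by eye, the error is about 8.5% to 15% when all subjects have two eligible eyes and about 7% to 12% when half do, for assumed inter-eye correlations of 0.3 to 0.8. Unpaired, it is about 0.5% to 12%, and any agreement with 5% would be accidental. The direction of the paired result needs only a positive correlation and some subjects with two eligible eyes; its size rests on the assumptions.

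The study-eye comparison is valid if paired. If run unpaired, power for 60 µm with 24 subjects would fall from 98% to between 94% and 65%, depending on the assumed between-subject SD. The missing period term is minor with balanced sequences. The GEE figures apply only if no small-sample correction is used, a point the plan leaves open. The plan should be changed on this point, but the study-eye comparison is not undermined.

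**What to change.** Delete the t-test on all eligible eyes from section 8.1.2 and the synopsis. For each dose against placebo, analyse one value per subject per period in a crossover model with treatment, period and a subject effect; a sequence term is optional. Use the study eye for the study-eye analysis and the mean of the eligible eyes for the all-eyes analysis, and say which one governs. The planned baseline adjustment can stay as a covariate. If the GEE is kept, state that it clusters on subject (both eyes and both visits) and uses a small-sample-corrected variance with a t reference.

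The cost is wording and one or two degrees of freedom, with no new data. Because the text is in the protocol, an amendment would need IRB approval under section 13.1. The all-eyes interval becomes wider than the eye-paired one by the factor √(1+ρ) × t(n−2)/t(2n−1) when everyone has two eligible eyes. At ρ = 0.3, 0.5 and 0.8 this is 1.18, 1.26 and 1.38 with 24 subjects, and 1.31, 1.41 and 1.54 with 8. With 24 subjects of whom half have two eligible eyes, it is about 1.14, 1.17 and 1.22. The extra width is uncertainty that the eye-level test leaves out.

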8.3 Level of Significance

Each hypothesis will be tested at a significance level of 0.05.

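### The all-eyes GEE has about 8, 16 or at most 24 subjects per dose comparison and no small-sample correction; run in the usual way it rejects too often, most clearly with 8.

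*Combined protocol and SAP*

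**What the plan says.** In the current protocol version, Section 8.1.2 and the synopsis (Pharmacodynamic Analysis) set the comparison dose by dose: "These parameters will be compared between each dose of P-321 Ophthalmic Solution and Placebo using a t-test for study eyes, and for all eligible eyes". ANCOVA adjusts for baseline in the study eye. For the wider set of eyes the plan adds: "For all eligible eyes, a generalized estimation equations (GEE) will also be used to account for the correlation between eyes". On the model it says only this: "For the GEE analysis, an exchangeable correlation matrix will be assumed".

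The numbers behind each comparison come from Section 4.1. On Phase 1 it states: "Approximately 8 subjects participating in Phase 1 will receive 0.017% P-321 ophthalmic Solution and Placebo". Phase 2 takes whoever is left of the planned total, at a strength chosen after the Phase 1 data review: "and the remainder of the 24 subjects participating in Phase 2 will receive either 0.05%, 0.017% or 0.01% P-321 and placebo". Section 8.2 gives the total: "An initial sample size of approximately 24 subjects is proposed for this study". Section 8.3 sets the level: "Each hypothesis will be tested at a significance level of 0.05".

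The plan does not state what forms a cluster (the subject, or the subject at one visit), whether standard errors are robust or model-based, whether a small-sample correction applies, which reference distribution is used, or whether period enters the model.

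**The concern.** There are two all-eyes analyses. The plain t-test makes no stated allowance for two eyes of one person, so the GEE is what should give the all-eyes result a valid error rate. GEE inference is justified for many independent clusters, and here the clusters are people. With few of them, the ordinary sandwich standard error is biased downward, and a normal critical value ignores the uncertainty in that standard error. Both push the test towards rejecting too often and make confidence intervals too narrow. The smallest set is the 8-subject Phase 1 group, and comparing strengths is a secondary objective (Section 3).

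**Working it through.** **The plan's own figure.** The plan gives no error rate for the GEE. Its only figure that can be checked here is the 98% power in Section 8.2 for 60 µm at 1 hour, SD 71 and about 24 subjects. Reading 71 as the SD of the within-subject difference, 60 × √24 / 71 = 4.14 and Φ(4.14 − 1.96) = 98.5% (97.7% with a t reference), so the figure reproduces. If 71 is the within-subject SD, as worded, the SD of the difference is 71√2 and power is 83% (80% with t). Either way the figure describes a paired comparison of all 24 subjects, not a GEE by dose.

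**Inputs.**
- Subjects per comparison: 8 (Phase 1), 24 − 8 = 16 (Phase 2), or 24 if Phase 2 keeps 0.017% or doses are pooled.
- Level 0.05, taken as two-sided because sidedness is not stated.
- Eligible eyes: one or two per subject (Section 5.1, criterion 5).
- Between-eye and between-visit correlations are not given, so they are assumptions below.

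**Closed form: subject as cluster, sandwich SE, normal reference.** With balanced data, the GEE estimate is the mean within-subject difference of eye-averaged values. The uncorrected sandwich variance divides by n where the usual estimate divides by n − k (k = 1 without a period term, 2 with it). The test therefore rejects when |t(n−k)| > 1.96 × √((n−k)/n), and its true size is

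P( |t(n−k)| > 1.96 × √((n−k)/n) ).

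| n | No period term: cut-off, size | Period term: cut-off, size |
|---|---|---|
| 8 | 1.96√(7/8) = 1.83, 10.9% | 1.96√(6/8) = 1.70, 14.1% |
| 16 | 1.96√(15/16) = 1.90, 7.7% | 1.96√(14/16) = 1.83, 8.8% |
| 24 | 1.96√(23/24) = 1.92, 6.8% | 1.96√(22/24) = 1.88, 7.4% |

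No correlation appears in the formula, so the working matrix is not the cause of this inflation.

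**Simulation under no effect.** There were 2,000 runs per case (Monte Carlo error about 0.5–0.8 points). All or some subjects had two eyes, and models were run with and without period, sequence and baseline terms. Rejection rates were 10.4–16.8% at n = 8, 8.4–10.2% at n = 16 and 5.9–8.7% at n = 24. The mean sandwich SE was 0.78–0.91, 0.88–0.95 and 0.91–0.99 of its true value. Rates were similar when the correlation was truly exchangeable and when eyes at one visit were more alike. Two further simulation sets gave 11–16% and 13–15% at n = 8, 8–10% and 7–12% at n = 16, and 6–8% and 7–8% at n = 24. Together the ranges are about 10–17%, 7–12% and 6–9%.

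**Other readings the text allows.**
- Model-based SE, subject as cluster: 4.8–7.8% if the correlation is truly exchangeable, and 6.8–14.0% if eyes at one visit are more alike. A further set, with a between-eye correlation of the visit deviation of 0.3–0.6, gave 8–17%. In a crossover, a single value must serve for two eyes at one visit, one eye at two visits, and opposite eyes at two visits.
- Subject-visit as cluster: 0.4–2.1% without baseline adjustment, with the SE about 1.3–1.5 times too large because the pairing of a person's two visits is ignored; 2.6–10.4% with baseline adjustment.

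**Alternatives.** Averaging eligible eyes per subject and visit, then applying the two-sequence crossover t-test, gave 4–6%; the assumptions were 60% or 100% of subjects with two eligible eyes and SD 71 µm for the one-eye between-visit difference. GEE with the Mancl-DeRouen variance and a t reference on n minus the number of parameters gave 0.7–3.4% at n = 8, 2.8–4.6% at n = 16 and 3.3–5.3% at n = 24.

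**The case against.** The strongest reply is that the plan does not commit to the calculation criticised. It names neither the cluster nor the variance estimator. Its stated purpose, allowing for correlation between eyes, also fits subject-visit clusters, under which the test can be conservative. A reader might infer that the planned standard errors are too small as a matter of fact; the text does not settle even the direction of the error. This stands, and it makes the rates conditional. It does not clear the plan, because the subject-visit reading is also miscalibrated.

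A reader might also blame the exchangeable matrix for the small sandwich SE. The documents and the arithmetic do not support that: the inflation is about the same when exchangeability is true. The matrix matters for model-based SEs, and how much depends on correlations the documents do not give.

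Third, the consequence is limited. The GEE is an additional analysis. The study-eye t-test and ANCOVA use one eye per subject (Section 5.4) and so have no between-eye problem. Section 8.1.3 says no efficacy endpoint will be formally assessed, and the dose criteria in Section 6.5 and Appendix XIV are not tied to a GEE p-value. Section 8.2 powers the study on all subjects, where the sandwich inflation is slight. These points stand and lower the severity. Against them, Section 4.2.1 names a primary endpoint measured by UHR-OCT, Section 8.3 sets a test level and Section 8.1.2 asks for each dose separately, so p-values and intervals at the smaller sizes are to be expected.

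**Conclusion.** The concern holds conditionally and should be fixed. With the subject as cluster, an uncorrected sandwich SE and a normal reference, the nominal 5% test has a true size of about 10–17% with 8 subjects, 7–12% with 16 and 6–9% with 24. The closed-form part rests only on balanced, normally distributed data; the outer ends of the ranges rest on assumed variance components and covariate sets. Model-based SEs run from about 5% to 17%, with the marked excess arising when eyes at one visit are more alike than exchangeability allows.

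Two stronger conclusions are not supported. A rate near 17% for the sandwich test belongs to 8 subjects only, and at 24 the excess is slight. The trial's main inference is not shown to be invalid, since the study-eye analyses do not share the fault.

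**What to change.** In Section 8.1.2 and the synopsis, replace the GEE sentences with one of these:

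1. **Preferred for simplicity:** average the eligible eyes within each subject and visit, and analyse with the two-sequence crossover t-test.
2. A linear mixed model with random effects for subject, eye within subject and visit within subject, fixed effects for treatment and period, and Kenward-Roger degrees of freedom.

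If GEE is kept, state the subject as cluster, a period term, a bias-corrected variance such as Mancl-DeRouen, and a t reference. Note in the plan that this is conservative with 8 subjects (about 1–4%), which costs power in the smallest set.

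The change needs wording and a little programming, but no new data, visits or subjects. Intervals become wider. Relative to the uncorrected version with a period term and balanced data, the factor is (t critical value / 1.96) × √(n/(n−2)):
- n = 8: (2.447/1.96) × √(8/6) = 1.44
- n = 16: (2.145/1.96) × √(16/14) = 1.17
- n = 24: (2.074/1.96) × √(24/22) = 1.11
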